### 5.2.5 Other safety parameters

In case of an infusion reaction monitor the patient per standard of care, grade the intensity of the reaction according to RCTC grading (cf. ISF) and proceed as described in [Section 4.2.2.1](#). Also draw plasma sample for IgE and ADA (anti-drug antibodies), as detailed in the CTP [Section 5.2.3](#) and the lab manual.

All cases of malignancies that are detected during the trial will be reported as SAEs. Patients with a history of malignancy (except for specific cancers) will be excluded from this trial per the exclusion criteria ([Section 3.3.3](#)).

### 5.2.6 Assessment of adverse events

#### 5.2.6.1 Definitions of AEs

##### **Adverse event**

An adverse event (AE) is defined as any untoward medical occurrence in a patient or clinical investigation subject administered a medicinal product and which does not necessarily have to have a causal relationship with this treatment.

An AE can therefore be any unfavourable and unintended sign (including an abnormal laboratory finding), symptom, or disease temporally associated with the use of a medicinal product, whether or not considered related to the medicinal product.

##### **Serious adverse event**

A serious adverse event (SAE) is defined as any AE which fulfils at least one of the following criteria:

- results in death,
- is life-threatening, which refers to an event in which the patient was at risk of death at the time of the event; it does not refer to an event that hypothetically might have caused death if more severe.
- requires inpatient hospitalisation or
- requires prolongation of existing hospitalisation,
- results in persistent or significant disability or incapacity, or
- is a congenital anomaly / birth defect,
- or
- is deemed serious for any other reason if it is an important medical event when based on appropriate medical judgement which may jeopardise the patient and may require medical or surgical intervention to prevent one of the other outcomes listed in the above definitions.

Examples of such events are intensive treatment in an emergency room or at home for allergic bronchospasm, blood dyscrasias or convulsions that do not result in hospitalisation or development of dependency or abuse.

For Japan only: the following events will be handled as “deemed serious for any other reason”. AEs which possibly lead to disability will be reported as SAEs.

#### **AEs considered “Always Serious”**

Cancers of new histology and exacerbations of existing cancer must be classified as a serious event regardless of the duration between discontinuation of the drug and must be reported as described in [Section 5.2.6.2](#), subsections “AE Collection” and **AE reporting to sponsor and timelines**”

In accordance with the European Medicines Agency initiative on Important Medical Events, Boehringer Ingelheim has set up a list of further AEs, which by their nature, can always be considered to be “serious” even though they may not have met the criteria of an SAE as defined above.

The latest list of “Always Serious AEs” can be found in the eDC system. A copy of the latest list of “Always Serious AEs” will be provided upon request. These events should always be reported as SAEs as described above.

#### **Adverse events of special interest (AESIs)**

The term AESI relates to any specific AE that has been identified at the project level as being of particular concern for prospective safety monitoring and safety assessment within this trial, e.g. the potential for AEs based on knowledge from other compounds in the same class. AESIs need to be reported to the sponsor’s Pharmacovigilance Department within the same timeframe that applies to SAEs, please see above.

The following are considered as AESIs:

- Systemic hypersensitivity including infusion reaction and anaphylactic reaction
  - Any suspicion of severe infusion reaction and of any potential cases of anaphylaxis should be defined and assessed using the criteria discussed in the statement paper from Sampson HA ([Appendix 10.7 R11-4890](#)).
- Severe infections (according to RCTC grading in [Appendix 10.8](#))
- Opportunistic and mycobacterium tuberculosis infections
  - These include pneumocystis jirovecii, BK virus disease including PVAN, CMV, post-transplant lymphoproliferative disorder (EBV), progressive multifocal leucoencephalopathy, bartonellosis (disseminated only), blastomycosis, toxoplasmosis, coccidioidomycosis, histoplasmosis, aspergillosis (invasive only), candidiasis (invasive or pharyngeal), cryptococcosis, other invasive fungi (mucormycosis (zygomycosis, rhizopus, mucor, lichtheimia), scedosporium/pseudallescheria boydii, fusarium), legionellosis, listeria monocytogenes (invasive only), tuberculosis, nocardiosis, non-tuberculous

mycobacterium, salmonellosis (invasive only), HBV reactivation, herpes simplex (invasive only), herpes zoster, strongyloides (hyperinfection syndrome and disseminated forms only), paracoccidioides, penicillium marneffeii, sporothrix schenckii, cryptosporidium species (chronic only), microsporidiosis, leishmaniasis (visceral only), trypanosoma cruzi infection (Chagas' disease) (disseminated only), campylobacteriosis (invasive only), shigellosis (invasive only), vibriosis (invasive due to vibrio vulnificus), HCV progression [[R17-2617](#)]

### Hepatic injury

A hepatic injury is defined by the following alterations of hepatic laboratory parameters:

- a. ALT or AST >5x ULN
- b. ALT or AST >3x ULN with the appearance of fatigue, nausea, vomiting, right upper quadrant pain or tenderness, fever, rash, and/or eosinophilia (> 5%)
- c. AST and/or ALT  $\geq$ 3 fold ULN combined with an elevation of total bilirubin  $\geq$ 2 fold ULN measured in the same blood draw sample

These lab findings constitute a hepatic injury alert and the patients showing these lab abnormalities need to be followed up according to the "DILI checklist" provided in the ISF. In case of clinical symptoms of hepatic injury (icterus, unexplained encephalopathy, unexplained coagulopathy, right upper quadrant abdominal pain, etc.) without lab results (ALT, AST, total bilirubin) available, the investigator should make sure these parameters are analysed, if necessary in an unscheduled blood test. Should the results meet the criteria of hepatic injury alert, the procedures described in the DILI checklist should be followed. If an alternative cause for the hepatic injury cannot be identified in the follow-up assessments specified in the "DILI checklist", discontinuation of treatment with study drug should be considered.

### Intensity (severity) of AEs

The intensity grading of AEs will be performed according to Rheumatology Common Toxicity Criteria (RCTC) Version 2.0 developed by OMERACT [[R13-3515](#)]. Refer to the ISF for intensity/severity classification. Intensity options are:

Grade 1	mild
Grade 2	moderate
Grade 3	severe
Grade 4	life-threatening

### Causal relationship of AEs

Medical judgement should be used to determine the relationship, considering all relevant factors, including pattern of reaction, temporal relationship, de-challenge or re-challenge, confounding factors such as concomitant medication, concomitant diseases and relevant history.

Arguments that may suggest that there is a reasonable possibility of a causal relationship could be:

- The event is consistent with the known pharmacology of the drug.
- The event is known to be caused by or attributed to the drug class.
- A plausible time to onset of the event relative to the time of drug exposure.
- Evidence that the event is reproducible when the drug is re-introduced
- No medically sound alternative aetiologies that could explain the event (e.g. pre-existing or concomitant diseases, or co-medications).
- The event is typically drug-related and infrequent in the general population not exposed to drugs (e.g. Stevens-Johnson syndrome).
- An indication of dose-response (i.e. greater effect size if the dose is increased, smaller effect size if dose is diminished).

Arguments that may suggest that there is no reasonable possibility of a causal relationship could be:

- No plausible time to onset of the event relative to the time of drug exposure is evident (e.g. pre-treatment cases, diagnosis of cancer or chronic disease within days / weeks of drug administration; an allergic reaction weeks after discontinuation of the drug concerned)
- Continuation of the event despite the withdrawal of the medication, taking into account the pharmacological properties of the compound (e.g. after 5 half-lives).
- Of note, this criterion may not be applicable to events whose time course is prolonged despite removing the original trigger.
- Additional arguments amongst those stated before, like alternative explanation (e.g. situations where other drugs or underlying diseases appear to provide a more likely explanation for the observed event than the drug concerned).
- Disappearance of the event even though the trial drug treatment continues or remains unchanged.

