#### Clinical PK/PD studies

BI655130 (SPESOLIMAB) or placebo (PBO) was administered to 78 healthy volunteers at single ascending i.v. doses from 0.001 mg/kg to 10 mg/kg body weight. Safety and tolerability of all tested i.v. doses was good. There were no drug-related SAEs. AEs categorized as related to treatment were observed in 3/19 (15.8%) subjects in the placebo group and in 7/59 (11.9%) subjects treated with BI655130 (SPESOLIMAB). The most frequent treatment-emergent AEs were nasopharyngitis (BI655130 (SPESOLIMAB): 21%; PBO: 15%), headache (BI655130 (SPESOLIMAB): 9%; PBO: 15%), influenza like illness (BI655130 (SPESOLIMAB): 7%; PBO: 10%), and diarrhoea (BI655130 (SPESOLIMAB): 3%; PBO: 10%). There were two AEs of moderate intensity (injection site haematoma, headache), all remaining AEs were of mild intensity. There was no apparent relationship between the frequency of AEs and the dose. There were no relevant changes compared to placebo for laboratory safety, including clinical chemistry, haematology, coagulation parameters, and urinalysis. No clinically relevant changes were observed in 12 lead ECGs, vital signs, and cardio-monitoring.

PK analysis showed that exposure ( $AUC_{0-tz}$  and  $C_{max}$ ) to BI655130 (SPESOLIMAB) increased with increasing dose in an approximately dose-proportional manner from 0.3 to 10 mg/kg. The effective half-life of BI655130 (SPESOLIMAB) is approximately 4 weeks in the linear dose range. Overall, PK data so far suggests target-mediated drug disposition (TMDD) kinetics for BI655130 (SPESOLIMAB). Anti-drug antibodies (ADA) were detected in 8 patients, 3 of those had pre-existing levels. Pharmacodynamic effects in this FIH Single Rising Dose trial [[c03361085-07](#)] were assessed by indirect target engagement (ITE) of IL36R by BI655130 (SPESOLIMAB) using an ex-vivo whole blood stimulation assay. All doses higher than 0.001 mg/kg were biologically active, corresponding to the minimum anticipated biological effect level, MABEL.

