#### Systemic hypersensitivity including infusion reaction and anaphylactic reaction

In case of systemic hypersensitivity including infusion reactions and anaphylactic reaction emerging during or after infusion of study drug, the investigator should consider in accordance with severity of the reaction and local standard of care to

- Immediately interrupt the infusion
- Treat with systemic anti-histamines, intravenous steroids, and in case of a severe allergic reaction (e.g., anaphylactic reaction) epinephrine

Also draw a plasma sample for IgE and ADA as detailed in the Lab Manual (Section 10 of the ISF). Consider also the evaluation of histamine, serum tryptase, and complement components.

In case of systemic hypersensitivity including infusion reaction and anaphylactic reaction, based on patient's clinical course and medical judgment, the infusion may be re-initiated in case of mild or moderate infusion reactions (according to RCTC grading of "allergic reaction / hypersensitivity" in ISF) at lower speed with gradual increase to complete the infusion as detailed in the Instructions for Preparation and Handling of BI655130 (SPESOLIMAB)/Placebo in the Investigator Site File.

In case of anaphylactic reaction based on the criteria discussed in the statement paper from Sampson HA ([Appendix 10.7 R11-4890](#)) suspected to be caused by the trial medication, the investigator should discontinue treatment with study drug

When a non-acute hypersensitivity reaction related to immune complexes (i.e., serum sickness) is suspected, please draw a sample for the laboratory assessment for circulating immune complexes.

Severe infections (according to RCTC grading in [Appendix 10.8](#)), serious infections, opportunistic or mycobacterium tuberculosis infection

- Treatment of the infection should be initiated promptly according to local standard of care. No further trial medication should be administered until the active infection has resolved. Treatment with study drug may be restarted when the patient has recovered according to investigator's assessment.

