#### 5.2.6.2 Adverse event collection and reporting

##### **AE Collection**

[figure not shown]
The investigator shall maintain and keep detailed records of all AEs in the patient files. The following must be collected and documented on the appropriate CRF(s) by the investigator:

- From signing the informed consent onwards until the first dose of trial medication in the extension trial:
    - all AEs (non-serious and serious) and all AESIs.
  - For patients not rolling over into subsequent open label extension studies:
    - from signing the informed consent onwards until the individual patient's end of trial( including 16 weeks follow-up visit after last treatment dose) :
    - all AEs ( non-serious and serious) and all AESIs.
- After the individual patient's end of the trial:  
the Investigator does not need to actively monitor the patient for AEs but should only report any occurrence of cancer and trial treatment related SAEs and trial treatment

related AESIs of which the Investigator may become aware of by any means of communication, e.g. phone call. Those AEs should be reported on the BI SAE form, but not on the CRF.

Figure 5.2.6.2: 1 Adverse event collection and reporting

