### **7.3.5 Safety analyses**

Adverse events will be coded using the current version of Medical Dictionary for Regulatory Activities (MedDRA) coding dictionary. Standard BI summary tables and listings will be produced.

All treated patients will be included in the safety analysis. In general, safety analyses will be descriptive in nature and will be based on BI standards. No hypothesis testing is planned.

Statistical analysis and reporting of adverse events will concentrate on treatment-emergent adverse events. To this end, all adverse events occurring between start of treatment and end of the residual effect period will be considered ‘treatment-emergent’. The residual effect

period (REP) is defined as 16 weeks after the last dose of trial medication. Adverse events that start before first drug intake and deteriorate under treatment will also be considered as 'treatment-emergent'. The primary set of safety outputs will be done including data through the first 12 weeks of treatment (consistent with the timing of the primary efficacy analysis); further outputs will be also produced which include all safety data through the REP.

Frequency, severity, and causal relationship of adverse events will be tabulated by system organ class and preferred term after coding according to the current version of the Medical Dictionary for Drug Regulatory Activities (MedDRA).

Laboratory data will be analysed both quantitatively as well as qualitatively. The latter will be done via comparison of laboratory data to their reference ranges. Values outside the reference range as well as values defined as clinically relevant will be highlighted in the listings. Treatment groups will be compared descriptively with regard to distribution parameters as well as with regard to frequency and percentage of patients with abnormal values or clinically relevant abnormal values.

Vital signs, physical examinations, or other safety-relevant data observed at screening, baseline, during the course of the trial and at the end-of-trial evaluation will be assessed with regard to possible changes compared to findings before start of treatment.

Immunogenicity data will be analysed in a descriptive way.

[figure not shown]
#### Pooled Analyses of Parts 1 and 2

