Malignant tumours	(SMQ “Malignancies” – not for display) (Sub-SMQ “Malignant or unspecified tumours” – not for display) Narrow Sub-SMQ “Malignant tumours” Sub-SMQ “Haematological malignant tumours” Sub-SMQ “Non-Haematological malignant tumours”

Based on the specification provided in ICH E3 (17), the sponsor has defined AEs which are to be classified as ‘other significant’. For the current trial, these will include those non-serious AEs which were reported with ‘action taken = Drug Withdrawn’ or ‘action taken = Dose Reduced’.

The exposure-adjusted incidence rate and frequency of patients with AEs will be summarised by treatment, primary system organ class and preferred term. AEs which were considered by the investigator to be drug related will be summarised separately. Separate tables will also be provided for patients with SAEs, patients with drug-related AEs, patients with investigator-reported AESIs, patients with AE leading to discontinuation of the trial, patients with other significant AEs and User-defined Adverse Event Concepts (UDAEC) (see [Table 7.8.1: 1](#)). AEs will also be summarized by maximum intensity based on the RCTC measure (see [Section 5.4.1](#)).

For disclosure of AE data on ClinicalTrials.gov, the frequency of patients with non-serious AEs occurring with an incidence of greater than 5% (in preferred terms) will be summarised by treatment, primary system organ class and preferred term. The frequency of patients with SAEs will also be summarised.

For disclosure of AE data in the EudraCT register, the frequency of non-serious AEs with an incidence of greater than 5 % (in preferred terms) and the frequency of SAEs will be summarised.

7.8.2 **Laboratory data**

The analyses of laboratory data will be descriptive in nature and will be based on BI standards (18). Note that data from the central laboratory will be used for all displays described below, unless otherwise specified.

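### The causality guidance cites allergic onset weeks after stopping as evidence against a drug cause, which does not fit this antibody's half-life or its 16-week residual effect period

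*Protocol*

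**What the plan says.** Protocol section 5.2.6.1, under the causal relationship of AEs, first leaves the decision to the clinician: "Medical judgement should be used to determine the relationship, considering all relevant factors". Two lists follow. The second is introduced by "Arguments that may suggest that there is no reasonable possibility of a causal relationship could be". Its first item is a time to onset that is implausible relative to exposure, and one of the examples is "an allergic reaction weeks after discontinuation of the drug concerned". The next item concerns events that continue after withdrawal. It is limited by a reference to the compound's pharmacology, with five half-lives as the example. The onset item carries no such limit.

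Other sections describe the drug and the event:

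- Protocol 1.1: "The effective half-life of BI655130 (SPESOLIMAB) is approximately 4 weeks in the linear dose range". Section 4.1.2 works with about 4 to 5 weeks.
- Protocol 7.3.5: the residual effect "period (REP) is defined as 16 weeks after the last dose of trial medication". Adverse events starting within it are treatment-emergent.
- Protocol 4.2.1 provides for a delayed form: "When a non-acute hypersensitivity reaction related to immune complexes (i.e., serum sickness) is suspected", a sample for circulating immune complexes is to be drawn.
- Protocol 5.2.6.1 makes systemic hypersensitivity an AESI and does not restrict it to acute reactions.
- SAP 7.8.1: "AEs which were considered by the investigator to be drug related will be summarised separately".

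**The concern.** For a drug that clears in hours or days, an allergic reaction that begins weeks after stopping is hard to attribute to it, and the example is sensible. Here the same interval falls while a large part of the antibody is still in the body, and while the protocol itself still counts events as treatment-emergent. An investigator who takes the example at face value could call a delayed hypersensitivity reaction unrelated because of timing alone.

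The example appears only on the list of arguments against a drug cause, so any influence runs one way, towards understating drug-related hypersensitivity. The outputs at stake are those that use the relatedness call: the separate summaries of drug-related events, and the judgement whether a serious event is a suspected reaction (Protocol 4.1.5.2 refers to SUSAR reporting).

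**Working it through.** **Inputs.** Half-life about 4 weeks (Protocol 1.1) or about 4 to 5 weeks (4.1.2). Residual effect period 16 weeks (7.3.5). Yardstick of five half-lives (5.2.6.1, item on continuing events). Last dose at week 8 and, for patients who do not roll over, end of study at week 24 (flow charts).

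**1. The plan's own figure.** Section 3.1.4 equates 16 weeks with around 4 to 5 half-lives. Number of half-lives = 16 / half-life.

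- Half-life 4 weeks: 16 / 4 = 4.0.
- Half-life 5 weeks: 16 / 5 = 3.2.

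The lower end is reproduced. Five half-lives in 16 weeks would need a half-life of 16 / 5 = 3.2 weeks, shorter than either stated value.

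**2. Drug remaining after the last dose.** Fraction = 0.5^(t / half-life), assuming first-order elimination.

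| Weeks since last dose | Half-life 4 weeks | Half-life 5 weeks |
|---|---|---|
| 2 | 71% | 76% |
| 4 | 50% | 57% |
| 8 | 25% | 33% |
| 12 | 13% | 19% |
| 16 | 6% | 11% |

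**3. The section's own yardstick.** Five half-lives = 5 × 4 = 20 weeks to 5 × 5 = 25 weeks. Both exceed the 16-week residual effect period. By the test applied to continuing events, an interval of a few weeks is too short to count against the drug.

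**4. Faster clearance in UC.** Section 4.1.2 expects higher clearance in these patients but gives no figure. Assume a half-life of 2 to 3 weeks. The fraction at 4 weeks is then 0.5^(4/2) = 25% to 0.5^(4/3) = 40%, and at 8 weeks 0.5^(8/2) = 6% to 0.5^(8/3) = 16%. Exposure falls sooner, but the first weeks after the last dose are still weeks of exposure.

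**5. Who is in the window.** For patients who complete dosing and do not roll over, week 12 to week 24 is 12 − 8 = 4 to 24 − 8 = 16 weeks after the last dose. Early discontinuers are also followed for 16 weeks after theirs.

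**6. What uses the relatedness call.**

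| Process or output | Depends on causality? |
|---|---|
| AE and AESI collection to the 16-week visit or first extension dose (Protocol 5.2.6.2) | No |
| SAE and AESI reporting within 24 hours (5.2.6.2) | No |
| Treatment-emergent AE tables (Protocol 7.3.5, SAP 7.8.1) | No |
| Investigator-reported AESI table (SAP 7.8.1) | No |
| Search-based hypersensitivity concepts, narrow SMQs (SAP Table 7.8.1: 1) | No |
| Drug-related AE summaries (SAP 7.8.1) | Yes |
| Suspected-reaction (SUSAR) assessment | Yes |

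**The case against.** The strongest reply is that this is guidance, not a rule. The lists say what may or could be argued, the parent criterion refers to exposure, and clinical judgement comes first. An investigator who knows the half-life can apply the criterion correctly. This stands, and it limits the claim to a nudge.

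It is also fair that the fraction of drug remaining is not the probability that an allergic reaction begins then, and that the residual effect period is a counting window and not a causality rule. The finding in section 1.1 of more than 90% peripheral receptor engagement for at least 22 weeks is a preliminary pharmacodynamic result in healthy volunteers and says little about allergy. For prior biologics, Appendix 10.6 bounds a delayed reaction at more than 24 hours and less than 15 days, which only partly overlaps with weeks after stopping. Late onset therefore remains a legitimate thing to weigh. None of this makes the example a good one for this antibody.

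A reader might infer three stronger points that the documents do not support:

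- *Lost reports.* Section 5.2.6.2 says that after a patient's end of trial the investigator "should only report any occurrence of cancer and trial treatment related SAEs" and related AESIs. This filter starts only after the visit 16 weeks after the last dose, when the residual effect period is over, or once dosing begins in the extension trial. It does not remove events from the period in question.
- *Resolution while treatment continues.* The same list counts disappearance of an event under unchanged treatment against a drug cause. One might apply this to infusion reactions, but section 4.2.1 describes interrupting, treating and possibly restarting more slowly. That is closer to de-challenge, which the guidance names as a factor to weigh.
- *A general rule.* Declaring time since last dose irrelevant for every event within 16 weeks would remove an ordinary part of causality assessment for events unconnected with hypersensitivity.

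Finally, the SAP records early termination and says that a seamless Part 2 is no longer viable. This reduces the practical reach, but the drug-related summaries are still planned for Part 1.

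**Conclusion.** The example is inconsistent with the protocol's half-life, its residual effect period, the delayed hypersensitivity it foresees, and the half-life qualifier on the neighbouring item. On the stated half-lives about half the drug remains 4 weeks after the last dose and a quarter to a third at 8 weeks. This rests on first-order elimination and on values that are not specific to UC. Under the assumed shorter half-lives the conclusion weakens at 8 weeks but holds at 4.

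The consequence is small. The wording can tilt a relatedness call on delayed hypersensitivity towards unrelated, and that call reaches only the drug-related AE summaries and the SUSAR assessment. The number of events affected cannot be given, because the documents contain no rate of delayed hypersensitivity. The overall hypersensitivity estimates come from tables that ignore causality and are not affected, and no efficacy analysis, sample size or error rate is involved.

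**What to change.** In Protocol section 5.2.6.1, either delete the allergic-reaction example from the onset item, or give that item the same pharmacological limit, with five half-lives as the illustration, that the next item already has. State the half-life beside it so that sites can apply it. The intended result is that, for hypersensitivity events within the residual effect period, time since the last dose is not by itself an argument against causality. Other event types and the remaining items on the list stay as they are. Notify sites of the change.

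The cost is a wording amendment and a site notice. Slightly more events may be classed as drug-related.
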